5.2.13 Radiation Therapy Adverse Events

Acute

Expected acute radiation-induced toxicities include hair loss, fatigue, and erythema or soreness of the scalp. Potential acute toxicities include nausea and vomiting as well as temporary aggravation of brain tumor symptoms such as headaches, seizures, and weakness. Reactions in the ear canals and on the ear should be observed and treated symptomatically; these reactions could result in short-term hearing impairment. Dry mouth or altered taste have been occasionally reported.

Early Delayed

Possible early delayed radiation effects include lethargy and transient worsening of existing neurological deficits occurring 1 – 3 months after radiotherapy treatment.

Late Delayed

Possible late delayed effects of radiotherapy include radiation necrosis, endocrine dysfunction, and radiation-induced neoplasms. In addition, neurocognitive deficits, which could lead to mental slowing and behavioral change, are possible. Permanent hearing impairment and visual damage are rare. Cataracts can be encountered.

5.3 Temozolomide (TMZ)

Because TMZ as prescribed in this study is considered the standard-of-care (SOC) treatment for this indication, commercial sources will be used for TMZ drug supply, unless otherwise mandated by the country. AbbVie may provide or reimburse for TMZ to participating sites as required based upon availability or local regulations.

5.3.1 TMZ Administration

5.3.1.1 Chemoradiation

TMZ will be administered continuously from Day 1 of radiotherapy to the last day of radiation at a daily oral dose of 75 mg/m² (for a maximum of 49 days). The timing of each daily dose will be at the discretion of the Investigator.

The dose will be determined using actual body surface area (BSA) as calculated in square meters at the beginning of the concomitant treatment. The BSA will be calculated from the height

obtained at the screening visit and the weight obtained at the visit immediately before the first day of treatment. The dose of TMZ does not have to be adjusted unless there has been at least a 10% change in body weight; recalculation of dose for < 10% weight changes is allowed at the discretion of the Investigator. Recalculations for subsequent changes in height are permissible but not required. The dose will also not be capped for those that are overweight. The daily dose will be rounded to the nearest 5 mg. The exact dose administered should be recorded in the eCRF. Each daily dose should be given with the least number of capsules.

Subjects should be instructed to swallow the capsules whole, in rapid succession, without chewing them. If vomiting occurs during the course of treatment, no re-dosing of the subject is allowed before the next scheduled dose. The capsules should be taken on an empty stomach, therefore a minimum of 2 hours after eating and with no food consumption for at least 1 hour after TMZ administration.

Antiemetic prophylaxis is usually not required for the continuous daily dosing schedule (during radiation). However, prophylaxis with a 5-hydroxytryptamine₃ (5-HT₃) antagonist is recommended prior to administration of the first few TMZ doses and should be administered orally 30 to 60 minutes before TMZ treatment. Most subjects report optimal nausea control with the use of a 5-HT₃ antagonist. Routine use of antiemetics is recommended during the adjuvant phase of treatment.

IV temozolomide (as per local institutional standard) may be used instead of oral TMZ if there is a change in the subject's social situation (e.g., move to a nursing home or changes in drug reimbursement) after treatment TMZ initiation such that oral dosing of temozolomide is no longer possible.

5.3.1.2 Adjuvant Treatment

TMZ will be administered orally once per day for 5 consecutive days (Days 1 – 5) of a 28-day (+/- 3 day) cycle. The starting dose for the first cycle will be 150 mg/m²/day, with a single dose escalation to 200 mg/m²/day in subsequent cycles if no treatment-related adverse events > Grade 2 are noted. The timing of each daily dose will be at the discretion of the Investigator.

The start of the first cycle will be scheduled approximately 28 days after the last day of radiotherapy. The start of all subsequent cycles (Cycles 2 – 12) will be scheduled every 4 weeks (28 days ± 3 days) after the first daily dose of TMZ of the preceding cycle.

The dose will be determined using the BSA calculated at the beginning of each treatment cycle. The BSA will be calculated from the height obtained at the screening visit and from the weight

obtained at the visit immediately before each cycle. More frequent assessment and use of height and/or weight and calculation of BSA are permitted throughout the study. The dose of TMZ does not have to be adjusted unless there has been at least a 10% change in body weight; recalculation of dose for < 10% weight changes is allowed at the discretion of the Investigator. The dose will also not be capped for those that are overweight. The daily dose will be rounded to the nearest 5 mg (where dosage strengths are available to accommodate rounding to 5 mg). The exact dose administered should be recorded in the eCRF. Each daily dose should be given with the least number of capsules.

Prior to each treatment cycle with TMZ a complete blood count (CBC) will be obtained (within 72 hours prior to dosing). Subjects should be instructed to fast at least 2 hours before and 1 hour after TMZ administration. Water is allowed during the fast period. Subjects will be instructed to swallow the capsules whole, in rapid succession, without chewing them.

If vomiting occurs during the course of treatment, no re-dosing of the subject is allowed before the next scheduled dose.

Antiemetic prophylaxis with a 5-HT3 antagonist is strongly recommended and should be administered 30 to 60 minutes before TMZ administration (Section 5.8).

IV temozolomide (as per local institutional standard) may be used instead of oral TMZ if there is a change in the subject's social situation (e.g., move to a nursing home or changes in drug reimbursement) after treatment TMZ initiation such that oral dosing of temozolomide is no longer possible.

Subjects will be treated with post-radiation TMZ for 6 cycles unless there is evidence of tumor progression (RANO) or treatment-related toxicity (Section 8.3).

Subjects demonstrating continued benefit and no unacceptable toxicity from adjuvant TMZ may continue TMZ for an additional 6 cycles (12 cycles in total) at the discretion of the investigator if this is considered an acceptable standard of care per local regulations. TMZ treatment for more than 12 cycles will not be allowed.

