8.3 Temozolomide Toxicity Management

TMZ should be administered per the local prescribing regulations. If local prescribing information and the instructions in Section 8.3.1 or Section 8.3.2 conflict, then either local prescribing information or protocol language can be used at the discretion of the investigator.

See Section 8.4 for guidelines on repeat testing and evaluation of hepatic laboratory abnormalities regardless of the assessed relationship to study treatments.

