8.3.2 Post-Radiation (Adjuvant) Temozolomide

Continued dosing administration is based on adverse events (AEs) during the prior treatment cycle. If multiple AEs are seen, the dose administered should be based on the dose reduction required for the most severe grade of any single AE.

Dose Level	Temozolomide Dose, mg/m ² /day	Remarks
-1	100	Reduction if prior AE
0	150	Starting dose cycle 1 (adjuvant)
+1	200	Escalated dose at cycle 2, for cycles 2 – 12 in absence of AE

Delay

On Day 1 of each cycle (within the prior 72 hours), ANC $\geq 1.5 \times 10^9/L$, platelet count $\geq 100 \times 10^9/L$ and all treatment-related grade 3 or 4 non-hematologic AEs (except alopecia, nausea, and vomiting) must have resolved (to grade ≤ 1).

If AEs persist, treatment should be delayed by 2 weeks for up to 4 consecutive weeks, so that the TMZ dosing can coincide with the administration of the ABT-414 or placebo. If, after 4 weeks of delay, all AEs have still not resolved, then any further adjuvant treatment with TMZ should be stopped. When possible, TMZ treatment when resumed should start on either Day 1 or Day 15 of a cycle so that it may coincide with ABT-414/placebo treatment.

Dose Escalation

If, during the first cycle, all non-hematologic AEs observed were grade ≤ 2 (except alopecia, nausea and vomiting) and with platelets $\geq 100 \times 10^9/L$ and ANC $\geq 1.5 \times 10^9/L$, then the TMZ dose should be escalated to dose level 1 and this dose should be used as the starting dose for subsequent cycles. If treatment after cycle 1 has to be delayed because of ongoing non-hematologic AEs of grade ≥ 2 , then no escalation is possible. If the dose was not escalated at cycle 2, then the dose should not be escalated in further cycles (Cycles 3 – 6).

Dose Reductions

If any non-hematologic AE observed was grade > 2 (except alopecia, nausea and vomiting) and/or if platelets $< 50 \times 10^9/L$ and/or ANC $< 1 \times 10^9/L$, then the dose should be reduced by one dose level. For subjects who would require dose reductions to a dose level $< 100 \text{ mg/m}^2/\text{day}$, TMZ will be stopped. Also, if any of the same non-hematologic grade 3 AE recurs (except alopecia, nausea and vomiting) after reduction for that AE, then TMZ will be stopped.

If any treatment-related non-hematologic AE observed was grade 4 (except alopecia, nausea and vomiting) then adjuvant TMZ treatment should be stopped.

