Subsequent cycles (Cycles 3 – 12): Any dose reductions of TMZ will be determined according to (1) non-hematologic AE during the preceding treatment cycle, as well as (2) the nadir (lowest/worst) ANC and platelet counts observed. No dose escalation should be attempted. The same dose reductions as for the second cycle should be applied.

Important: If the dose was reduced or delayed for adverse events, there will be no dose escalation.

The reason(s) for dose reduction and/or delay must be documented in the eCRF.

Summary of Dose Modification or Discontinuation During Post-Radiation Temozolomide

Worst Non-Hematologic AE (Except Alopecia, Nausea and Vomiting) During the Previous Cycles	
Grade	Dose Modification
0 – 2	No dose modifications for non-hematologic AEs. Dose escalations (only for cycle 2) or reductions based on ANC and platelet counts are applicable.
3	Reduce by one dose level (except alopecia, nausea and vomiting). Dose modifications (escalations or reductions) based on ANC and platelet counts are not applicable. No further escalation is possible. If the same non-hematologic grade 3 AE recurs (except alopecia, nausea and vomiting) after reduction for that AE, then stop temozolomide.
4	Stop temozolomide (except for alopecia, nausea and vomiting). Dose modifications (escalations or reductions) based on ANC and platelet counts are not applicable.

Nadir Values

ANC	Action
$\geq 1.5 \times 10^9/L$	Escalation to DL 1 (cycle 2 only)
$\geq 1 \text{ \& } < 1.5 \times 10^9/L$	Dose unchanged
$< 1 \times 10^9/L$	Reduce by 1 dose level
Platelets	
$\geq 100 \times 10^9/L$	Escalation to DL 1 (cycle 2 only)
$50 - 99 \times 10^9/L$	Dose unchanged
$< 50 \times 10^9/L$	Reduce by 1 dose level

Note: A complete blood count must be performed on Day 22 (+/- 3 days) of each adjuvant treatment cycle.

Hematologic AE on Day 1 of Each Cycle (Within 72 Hours Before)

AE	Delay
ANC $< 1.5 \times 10^9/L$ and/or Platelet count $< 100 \times 10^9/L$	Delay up to 4 weeks until all resolved. If unresolved after 4 weeks then stop temozolomide. If resolved, dose delay/reductions based on non-hematologic AEs are applicable. If treatment has to be delayed for AEs, then no escalation is possible.

Non-Hematological AE (Except for Alopecia, Nausea and Vomiting) on Day 1 of Each Cycle (Within 72 Hours Before)

Grade	Delay

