11.4.1 Variables and Criteria Defining Abnormality

NCI CTCAE v. 4 grading criteria for laboratory abnormalities are shown in [Table 9](#) and [Table 10](#).

Table 9. Criteria for NCI CTCAE Grades for Laboratory Values Hematology Variables

	Units	NCI CTCAE Grade ≥ 3		NCI CTCAE Grade ≥ 4	
		Low	High	Low	High
Hematology Variables					
Hemoglobin	g/L	< 80	> ULN + 40		
White blood cell count	$10^9/L$	< 2		< 1	
Neutrophil count	$10^9/L$	< 1		< 0.5	
Lymphocyte count	$10^9/L$	< 0.5		< 0.2	
Absolute Platelet count	$10^9/L$	< 50		< 25	
Coagulation Variables					
INR increased	ratio		> $2.5 \times \text{ULN}^*$		

* Or baseline if on anticoagulation.

Table 10. Criteria for NCI CTCAE Grades for Laboratory Values - Chemistry Variables

Chemistry Variables	Units	NCI CTCAE Grade ≥ 3		NCI CTCAE Grade ≥ 4	
		Low	High	Low	High
Creatinine	mcmol/L		$> 3 \times \text{ULN}$		$> 6 \times \text{ULN}$
Total bilirubin	mcmol/L		$> 3 \times \text{ULN}$		$> 10 \times \text{ULN}$
Alanine aminotransferase (ALT/SGPT)	U/L		$> 5 \times \text{ULN}$		$> 20 \times \text{ULN}$
Aspartate aminotransferase (AST/SGOT)	U/L		$> 5 \times \text{ULN}$		$> 20 \times \text{ULN}$
Alkaline phosphatase (ALP)	U/L		$> 5 \times \text{ULN}$		$> 20 \times \text{ULN}$
Gamma glutamyl transferase (GGT)			$> 5 \times \text{ULN}$		$> 20 \times \text{ULN}$
Sodium	mmol/L	< 130	> 155	< 120	> 160
Potassium	mmol/L	< 3	> 6	< 2.5	> 7
Calcium	mmol/L	< 1.75	> 3.1	< 1.5	> 3.4
Glucose	mmol/L	< 2.2	> 13.9	< 1.7	> 27.8
Cholesterol	mmol/L		> 10.34		> 12.92
Triglycerides	mmol/L		> 5.7		> 11.4
Albumin	g/L	< 20			
Magnesium	mmol/L	< 0.4	> 1.23	< 0.3	> 3.3

Definition of Potentially Clinically Significant Laboratory Values

Laboratory values will be considered as potentially clinically significant if they are Grade 3 or higher as shown in [Table 4](#) and [Table 5](#), with the following exceptions:

- GGT: Grade 4
- Total bilirubin: $> 2 \times \text{ULN}$
- Concurrent ALT or AST $> 3 \times \text{ULN}$ and total bilirubin $\geq 2 \times \text{ULN}$

- Concurrent ALT or AST $> 3 \times \text{ULN}$, ALP $< 2 \times \text{ULN}$ and total bilirubin $\geq 2 \times \text{ULN}$

The maximum ratio relative to the ULN will be used to determine if subjects met the criteria listed above. The ALT, AST, and total bilirubin values need to be concurrent (i.e., collected on same date) and should be collected within 49 days following the last dose date of any study drug in order to meet the defined criteria.

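### Protocol Section 5.3.1.2 escalates adjuvant temozolomide to 200 mg/m² without the blood-count condition in Section 8.3.2, so the same patient can be escalated under one section and held at 150 under the other

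*Protocol*

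**What the plan says.** Two sections of the protocol set the rule for raising adjuvant TMZ.

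**Section 5.3.1.2 (administration).** The first cycle is given at 150 mg/m²/day. One step up to 200 mg/m²/day follows "in subsequent cycles if no treatment-related adverse events > Grade 2 are noted". A blood count is required before each cycle, but no threshold is attached to it and it is not linked to escalation.

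**Section 8.3.2 (toxicity management).** Three conditions apply to cycle 1: non-hematologic events of Grade 2 or lower (alopecia, nausea and vomiting excepted), platelets of at least 100 × 10⁹/L, and ANC of at least 1.5 × 10⁹/L. If all are met, "then the TMZ dose should be escalated to dose level 1 and this dose should be used as the starting dose for subsequent cycles". The nadir table in the same section gives "Dose unchanged" for platelets of 50–99 and for ANC from 1 to below 1.5. Escalation is possible at cycle 2 only, and "If the dose was reduced or delayed for adverse events, there will be no dose escalation". The dose-level table words the condition in a third way: 200 mg/m² is used "in absence of AE".

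**Links between the two.** Section 5.3.1.2 refers to Section 8.3 once, where it lists the grounds for giving fewer than 6 cycles: "evidence of tumor progression (RANO) or treatment-related toxicity (Section 8.3"). Section 8.3 has a conflict rule, but it addresses only disagreement between the local label and 8.3.1 or 8.3.2. In that case, "then either local prescribing information or protocol language can be used at the discretion of the investigator".

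**The concern.** Section 5.3.1.2 judges every treatment-related adverse event by one cut-off, Grade 2, with no exemptions. Section 8.3.2 judges marrow suppression by count thresholds that are stricter than that cut-off, and exempts three non-hematologic events from the grade test. Neither rule is contained in the other.

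What is at stake is patient safety and consistent dosing. A site that follows the administration section as written would raise the alkylator dose in a patient whose marrow suppression the protocol's own nadir table treats as a reason to hold it. The chemotherapy review in Section 5.3.2 also has no single standard for deciding whether a cycle 2 dose was per protocol.

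The point is no wider than that. The interim results in Protocol Section 1.0 give overall adverse event incidence, including more thrombocytopenia with ABT-414, but not cycle 1 nadirs. The INTELLANCE-2 summary in the same section reports similar neutropenia and thrombocytopenia with ABT-414/TMZ and with TMZ alone. No imbalance between arms is therefore claimed.

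**Working it through.** The plan gives no figure to reproduce. The check applies both rules to the same patients and then works out the dose difference.

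**Step 1: grade of the counts.** SAP Table 9 ("Criteria for NCI CTCAE Grades for Laboratory Values Hematology Variables", Section 11.4.1) starts Grade 3 at platelets below 50 and neutrophils below 1 × 10⁹/L. A platelet nadir of 50–99, or an ANC nadir from 1 to below 1.5, is therefore not above Grade 2.

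**Step 2: both rules side by side.** Counts are cycle 1 nadirs in 10⁹/L. Apart from the finding named in each row, no adverse event is above Grade 2.

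| Cycle 1 finding | Section 5.3.1.2 | Section 8.3.2 |
|---|---|---|
| Platelets ≥ 100 and ANC ≥ 1.5 | 200 | 200 |
| Platelets 50–99, recovered by cycle 2 Day 1 | 200 | 150, with no later escalation |
| ANC 1 to < 1.5, recovered by cycle 2 Day 1 | 200 | 150, with no later escalation |
| Either band, recovered only after a delay | 200 (no bar stated) | 150 (escalation barred after a delay) |
| Platelets < 50 or ANC < 1, treatment-related | No escalation | Reduced to 100 |
| Treatment-related Grade 3 vomiting, counts adequate | No escalation | 200 (vomiting exempt) |

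The rules agree that counts at or above the upper thresholds permit escalation and that Grade 3 counts do not. They disagree throughout the middle band, and they disagree in the other direction for vomiting. The same reversal applies to treatment-related nausea above Grade 2.

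**Step 3: dose difference for an affected patient.** TMZ is given on Days 1–5 of each cycle.

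- Per cycle: 200 × 5 = 1,000 mg/m² against 150 × 5 = 750 mg/m². The difference is 250 mg/m², and 250 / 750 = 33%.
- One cycle at 200, then a reduction to 150: 250 mg/m² in total.
- Cycles 2–6 at full dose: 5 × 250 = 1,250 mg/m² (5,000 against 3,750).
- Cycles 2–12 at full dose, if TMZ is extended: 11 × 250 = 2,750 mg/m² (11,000 against 8,250).

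The last two are ceilings that assume no later reduction, delay or progression. For scale, cycle 12 starts about 6 + 4 + 44 = 54 weeks after chemoradiation begins, which is 378 / 30.4375 = 12.4 months. The interim median PFS was 8.0 and 6.3 months in the two arms, so few patients could approach the 2,750 figure.

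**Step 4: number of patients affected.** The documents do not report how many patients had a cycle 1 nadir in either band, so no total is given.

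**The case against.** The strongest reply is that 5.3.1.2 cannot be used alone. It has no delay rule, no reduction step and no count threshold, so a site must open 8.3.2 to dose any cycle and will find the nadir table there. SAP Section 5.2.1 also points to Protocol Sections 8.1–8.3 for modifying TMZ doses. For blood counts the two sections can be read as cumulative, and applying both gives the safer 150. Other safeguards exist: weekly counts until recovery when platelets or ANC fall below the dosing thresholds (Protocol Table 2, footnote c), delay and reduction rules at later cycles, and ongoing chemotherapy review. TMZ may in any case follow the local label.

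Much of this stands. Most sites probably do follow 8.3.2, and the safeguards limit the harm from a wrong escalation. The vomiting case is not a safety problem for a site using 5.3.1.2, because there that section gives the lower dose. Main-study enrollment closed on 31 March 2018 (SAP Section 6.0), so most cycle 2 decisions have already been made and the point is less urgent.

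None of it decides which section prevails. The SAP reference is not addressed to sites and sets no precedence. The conflict rule in Section 8.3 does not mention 5.3.1.2. The cumulative reading also fails for vomiting: 8.3.2 directs escalation, so a site cannot satisfy both sections.

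**Conclusion.** The concern holds. As written, Section 5.3.1.2 escalates patients whom Section 8.3.2 holds at 150 mg/m²/day, and no text resolves the conflict. The bands affected are a cycle 1 platelet nadir of 50–99 × 10⁹/L and an ANC nadir from 1 to below 1.5 × 10⁹/L.

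The informative size is 250 mg/m², or 33%, per affected cycle. The totals of 1,250 and 2,750 mg/m² are upper limits. The conclusion rests on grading the counts by SAP Table 9 and on the patient having no other treatment-related event above Grade 2. It matters only at sites that use the protocol rule rather than local labelling. The textual conflict is certain; how often it changed a dose is unknown. It should be corrected because it concerns the dose of a myelosuppressive drug. No statistical property of the trial depends on it.

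**What to change.** In Section 5.3.1.2, replace the escalation condition with a statement that the dose rises to 200 mg/m²/day at cycle 2 only if the escalation criteria in Section 8.3.2 are met. In the Section 8.3.2 dose-level table, replace the remark "in absence of AE" with a reference to the same criteria.

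This keeps the rule the protocol already sets out in most detail. It also settles the delay and vomiting cases, because one set of criteria then covers all of them. The cost is one sentence and one table remark. Procedures, data collection and analysis do not change, and sites may still use the local label where Section 8.3 permits it.

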5.3.2 Chemotherapy Review

Chemotherapy reviews will be ongoing and performed by the Neuro-Oncology/Medical Oncology study chair or his/her designee.

5.4 ABT-414 / Placebo Treatment

During the Chemoradiation Phase, subjects in Arm A will receive blinded ABT-414 at 2.0 mg/kg IV infusion over 30 – 40 minutes once every 2 weeks (Day 1 of Weeks 1, 3, and 5 of the 6-week regimen). Subjects in Arm B blinded placebo IV infusion over 30 – 40 minutes once every 2 weeks (Day 1 of Weeks 1, 3, and 5 of the 6-week regimen). The dosing interval must be at least 12 days after the previous dose of ABT-414/placebo, and the doses must be administered no later than the last day of radiation treatment.

During the Adjuvant Therapy Phase, subjects in Arm A will receive blinded ABT-414 at 1.25 mg/kg on Day 1 (\pm 2 days) and Day 15 (\pm 2 days) of each 28-day cycle as a 30 – 40 minute infusion, and subjects in Arm B will receive blinded placebo IV infusion on Day 1 and Day 15 of each 28-day cycle for 12 cycles. If, after completing 12 cycles of study drug, the subject is tolerating the drug and the Investigator believes the subject is continuing to benefit from ongoing study drug treatment, the Adjuvant Phase may be extended following consultation with the Neuro-Medical Oncology Chair or AbbVie Medical Monitor. ABT-414/placebo will continue according to the same dosing schedule at the discretion of the Investigator as long as disease progression has not been determined.

The mg/kg dose will be determined from the weight on Day 1 of the Chemoradiation Phase and need not change during the Chemoradiation Phase unless there is a weight change by more than 10% from Week 1 Day 1. Recalculation of dose for < 10% weight changes is allowed at the discretion of the Investigator. There will be no cap on the weight of the subject or on the number of milligrams administered for overweight subjects. More frequent assessment and use of height and/or weight and calculation of BSA are permitted throughout the study.

If TMZ treatment is discontinued due to intolerance during either the Chemoradiation Phase or Adjuvant Phase, subjects will continue receiving study drug (ABT-414 or placebo) infusions according to the same study schedule.

The ABT-414 (active and placebo) will be provided as a lyophilized powder in vials. Each 100 mg vial of ABT-414 and placebo will be reconstituted with 5.0 mL of sterile water for injection to provide a 20 mg/mL ABT-414 active or a placebo solution. Each 20 mg vial of ABT-414 and placebo will be reconstituted with 1.0 mL of sterile water for injection to provide a 20 mg/mL ABT-414 active or a placebo solution. The ABT-414 is dosed as a fixed dose [or] based on body weight. The contents of two or more reconstituted vials may be diluted to accomplish the desired dose. The total volume administered will be dependent upon the assigned dose for that dosing period and/or the tolerability of the ABT-414/placebo. The

ABT-414 and placebo solution(s) will be administered via intravenous (IV) infusion. Specific dose preparation and documentation details will be provided to the site pharmacy outside of this protocol.

Guidelines for ABT-414 dose preparation, volume, and rate of infusion will be supplied by AbbVie to study site staff, within the study manual.

The dosing schedule for the hepatic impairment sub-study can be found in [Appendix IX](#).

